### 5.8.2 Analysis of Clinical Laboratory Measurements

Laboratory measurements include clinical chemistry, hematology and urinalysis results. Summaries of laboratory variables will include:

- Descriptive statistics of continuous laboratory result and change from baseline by visit
- Frequency and percentage summary for categorial lab data (urinalysis)
- The number (n) and percentage (%) of participants with abnormal lab value during study using a shift table
- Number (n) and percentage (%) of participants with CTCAE grade for key hematology parameters (white blood cell [WBC], neutrophils, lymphocytes, platelets, and hemoglobin)
- Number (n) and percentage (%) of participants with CTCAE grade for key serum chemistry parameters (alanine aminotransferase [ALT], aspartate aminotransferase [AST], serum creatinine, and bilirubin)

*Note: When participants have multiple CTCAE grades within the same parameters, the worst CTCAE grade will be considered. Refer [Appendix 11.4](#) for more details on CTCAE grading.*

All the above tables will be through the Week 36 visit.

Listing of all laboratory parameters original results, standard results, normal range, abnormal flag and CTCAE grade (whenever applicable) by participant and visit will be provided. Additionally, listings will be provided for pregnancy test, and tuberculosis test.

A line graph illustrating absolute values for key parameters will be presented by visit for each treatment group.

### 5.8.3 Analysis of Vital Signs

Summaries of vital sign variables will include:

- Descriptive statistics of vital sign variables and change from baseline by treatment and visits/timepoints
- Notable findings in vital signs will be summarized by treatment and visit/timepoint, which are defined as,
  - Temperature:  $>39.0$  degrees
  - An increase in Pulse Rate from baseline by  $\geq 25\%$  for on-treatment values  $>100$  beats/min
  - A decrease in Pulse Rate from baseline by  $\geq 25\%$  for on-treatment values  $<50$  beats/min.
  - Systolic BP  $\geq 140$  mmHg and increase by 20 mm Hg.
  - Diastolic BP  $\geq 90$  mmHg and increase by 10 mm Hg.
  - Systolic BP  $\leq 80$  mmHg and decrease by 20 mm Hg.
  - Diastolic BP  $\leq 50$  mmHg and decrease by 10 mm Hg.

All the above tables will be presented through the Week 36 visit.

A listing of vital signs data will be provided for each participant by treatment and visit.

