### **Treatment Period:** Day 1 (Baseline) to Day 113 (16 weeks)

Participants who meet all eligibility criteria will be enrolled and will receive three IV infusions of IMG-007 [REDACTED] or [REDACTED] administered 2 weeks apart at the Baseline (Day 1), Week 2 (Day 15), and Week 4 (Day 29) visits. The study site will contact participants by telephone approximately 24 hours after each infusion for assessment of AEs and/or concomitant medications.

On dosing days, study treatment will be administered as an IV infusion over approximately 60 minutes with a slower rate during the first 15 minutes. Participants will be closely monitored at the study site for a minimum of 1 hour after completion of each infusion or until any AEs observed during the observation have resolved or stabilized, whichever is longer. For diagnostic purposes, any participant who experiences any systemic infusion-related event should have a blood sample taken ideally 30–60 minutes after the onset for tryptase testing, and samples should be analyzed by a local laboratory if feasible. Study sites should have access to equipment or facilities for the management of potential hypersensitivity reactions.

Beyond dosing visits, participants will complete visits at Week 1 (Day 8), Week 6 (Day 43), Week 8 (Day 57), Week 12 (Day 85) and Week 16 (Day 113)/end of treatment (EOT).

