#### 4.6.3 Vital Signs and Physical Examination Variables

The following vital signs (VS) parameters will be collected:

- Systolic and diastolic blood pressure (mmHg)

- Pulse rate (bpm)
- Temperature (C)
- Respiratory rate (breaths/min)

Vital signs parameters will be collected as specified in the SoA ([Appendix 11.1](#)). On study treatment dosing days, i.e., Baseline (Day 1), Week 2 (Day 15), and Week 4 (Day 29), vital signs should be assessed before initiation of infusion; 15 ( $\pm$  5) minutes after the initiation of the infusion; 15 ( $\pm$  5) minutes after EOI, and 1 hour ( $\pm$  15 minutes) post EOI.

A complete physical examination will include, at a minimum, assessments of the skin, head and neck, cardiovascular, respiratory, gastrointestinal, and neurological systems. Measurement of weight, height, and BMI will be conducted only at baseline, unless any supplementary evaluations necessitate further measurements. All the assessment will be performed as specified in the SoA ([Appendix 11.1](#)).

A brief physical examination will include, at a minimum, assessments of the skin, lungs, cardiovascular system, and abdomen (liver and spleen). Symptom-directed physical examinations will be completed at each follow-up (including the extended follow-up) visit at the discretion of the investigator.

Investigators will be instructed to pay special attention to clinical signs related to previous serious illnesses. Unscheduled physical examinations can be conducted at the discretion of the PI or designee.

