### 6.1 Definition of Baseline for Efficacy/Safety Variables

Unless otherwise specified, the baseline assessment for all measurements will be the latest available valid measurement taken prior to the administration of study drug (Week 0 (Day 1)).

When it is not possible to determine the time of assessment, baseline value would be determined based on the measurement recorded on the day administration of the first dose of IMP.

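### Vital-sign changes after the Week 2 and Week 4 infusions are referred only to the Day 1 pre-dose value, so the tables cannot cleanly show acute change per infusion

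*SAP*

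**What the plan says.** SAP 4.6.3 and the vital-signs footnote of the protocol's Schedule of Assessments set four readings on each dosing day (Day 1, Day 15, Day 29). The first is before dosing: "vital signs should be assessed before initiation of infusion". The others come 15 minutes after the infusion starts, 15 minutes after it ends and 1 hour after it ends.

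SAP 6.1 defines one baseline, to apply unless something else is specified: "the baseline assessment for all measurements will be the latest available valid measurement taken prior to the administration of study drug", tied to Week 0 (Day 1).

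SAP 5.8.3 specifies nothing else. It plans "Descriptive statistics of vital sign variables and change from baseline by treatment and visits/timepoints", and then: "Notable findings in vital signs will be summarized by treatment and visit/timepoint, which are defined as". The pulse criteria name their reference ("An increase in Pulse Rate from baseline by" at least 25%, with an absolute limit). The blood-pressure criteria do not: the high-systolic one requires at least 140 mmHg "and increase by 20 mm Hg", without saying from what. SAP 6.1 supplies the only defined answer, which is Day 1.

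SAP 6.3 averages vital signs when a day has more than one observation, and does not exempt the timed dosing-day readings.

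**The concern.** The timed readings bracket each infusion. Protocol 6.6 lists infusion-related hypersensitivity among the key risks, with cardiovascular signs among its symptoms. The natural acute question is how far pulse and blood pressure moved from just before the infusion to during and after it.

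The planned summaries answer that for infusion 1 only. At Weeks 2 and 4 the change is the acute movement plus whatever shift has occurred since Day 1. A participant-level flag can then appear with no movement during the infusion, or fail to appear despite a clear one. Infusion 1 also has a different kind of reference from infusions 2 and 3, which blurs any comparison of acute changes across repeat dosing. The interim output list in SAP 7.1.1 includes notable vital-sign findings and shows no separate reference.

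**Working it through.** There is no stated figure to reproduce, so the check is of the text, followed by an illustration of size.

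**Scope.** Three post-start timepoints × 3 infusions = 9 readings per participant. The later two infusions account for 3 × 2 = 6 of them.

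**Age of the reference.** The doses are "administered 2 weeks apart at the Baseline (Day 1), Week 2 (Day 15), and Week 4 (Day 29) visits", so the gaps are 15 − 1 = 14 days and 29 − 1 = 28 days. With the 3-day early window and the permitted delays (5 days, or 10 for the last dose), the Week 2 gap runs from 12 − 1 = 11 to 20 − 1 = 19 days, and the Week 4 gap from 26 − 1 = 25 to 39 − 1 = 38 days.

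**Two hypothetical participants (systolic, mmHg).**
- Day 1 125, Week 4 pre-infusion 118, post-start 142. Within the visit: 142 − 118 = +24. Against Day 1: 142 − 125 = +17, so no flag.
- Day 1 118, Week 4 pre-infusion 139, post-start 140. Within the visit: 140 − 139 = +1. Against Day 1: 140 − 118 = +22, so flagged.

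**Model for size.** Reading = person mean + day effect (SD b) + reading error (SD w), with independent day effects and no average drift over time. Then
- variance of change from Day 1 = 2(b² + w²)
- variance of change from the same-visit pre-infusion reading = 2w²

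Assumptions, none of them in the documents: mean systolic 125 mmHg, between-person SD 12, b = 4 to 12, w = 4 to 6. Each setting was simulated with 400,000 participants, using the full rule (at least 140 and a rise of at least 20). Each cell gives the Day 1 reference, then the same-day reference.

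| b, w | SD of change (mmHg) | At least one false flag in 6 readings, no infusion effect | Full rule met per reading, true +25 mmHg |
|---|---|---|---|
| 4, 4 | 8.0 / 5.7 | 1.1% / 0.04% | 60.0% / 64.6% |
| 4, 6 | 10.2 / 8.5 | 4.4% / 2.0% | 56.6% / 58.3% |
| 8, 4 | 12.6 / 5.7 | 7.6% / 0.04% | 54.2% / 62.4% |
| 8, 6 | 14.1 / 8.5 | 11.9% / 2.0% | 53.0% / 56.4% |
| 12, 4 | 17.9 / 5.7 | 16.0% / 0.05% | 50.9% / 59.7% |
| 12, 6 | 19.0 / 8.5 | 20.1% / 2.1% | 50.4% / 54.1% |

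Example for the SD column, b = 8 and w = 4: √(2 × (64 + 16)) = 12.6 and √(2 × 16) = 5.7.

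For the 24 participants planned in Cohort 2, the expected number with at least one false high-systolic flag is 24 × 1.1% = 0.3 to 24 × 20.1% = 4.8 with the Day 1 reference. With the same-day reference it is 24 × 0.04% = 0.01 to 24 × 2.1% = 0.5.

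**Where the reference hardly matters.**
- Low systolic (at most 80 with a fall of 20): any reference of 100 or more meets the fall automatically, because 100 − 80 = 20. For a true fall of 45 mmHg, the flag fires in about 49 to 50% of readings with Day 1 and about 50% with the same-day reference.
- Pulse above 100 with a 25% rise: any reference of 80 or less meets the rise automatically (80 × 1.25 = 100). The reference matters only above that.
- Temperature: the criterion is absolute, so no reference enters.

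**The case against.** Change from one pre-treatment baseline is a coherent quantity: departure from the untreated state. It suits tables that run through Week 36. The Week 2 and Week 4 pre-infusion readings are already on drug, after one and two doses, so substituting them for Day 1 would subtract any cumulative effect. This stands, and it rules out replacing the Day 1 reference.

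The tables are also by timepoint, so pre- and post-infusion means appear for each dosing visit, and a listing is planned. With cohorts of 6 and 24, individual review is practical. This stands in part: a mean within-visit shift can be worked out by hand, but its SD and the participant-level flags cannot be read from the tables.

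Three stronger readings are tempting.
- A reader might infer that infusion reactions would be missed. The documents do not support this. SAP 4.6.1 and 5.8.1 summarise and list them as adverse events, and protocol 8.2.3.1 requires clinically significant vital-sign results to be reported as adverse events. The low-systolic flag also barely depends on the reference.
- A reader might infer that the safety review committee's outputs carry the same derivation. SAP 8 says they follow a separate document dated 11 April 2024, which is not available here, so this is unknown.
- A reader might quote the gain in sensitivity from the rise of 20 mmHg alone, about 60 to 65% against 72 to 81% at day-to-day SDs of 8 to 12. That leaves out the 140 mmHg limit. With the full rule the gap there is 50 to 54% against 54 to 62%.

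**Conclusion.** The point holds as a limited gap in a descriptive safety analysis. No planned change or change-based flag isolates the acute effect of infusions 2 and 3, although the reading needed for it is collected.

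The size rests wholly on assumed SDs. The reduction in false high-systolic flags is modest if day-to-day variation is small and large if it is 8 mmHg or more. The gain in detecting a true 25 mmHg rise is about 2 to 9 percentage points per reading. Under the model, the same-day reference did better on both measures in every setting tried. The primary endpoint, incidence of treatment-emergent adverse events, is unaffected. The change is worth considering, but the safety conclusions do not depend on it.

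**What to change.** Keep change from the Day 1 baseline as planned, and amend the SAP as follows.

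1. In 5.8.3, add change from the same-visit pre-infusion reading for every post-start timepoint on Day 1, Week 2 and Week 4.
2. Report the change-based pulse and blood-pressure notable findings against that reference as well, beside the Day 1 version.
3. State the reference for the blood-pressure criteria, which now name none.
4. In 6.3, limit same-day averaging of vital signs to repeats at the same timepoint. Read literally, it would blend pre- and post-infusion values, which conflicts with the by-timepoint summaries in 5.8.3.
5. Use the same derivation for the interim notable-findings output, and check the separate safety review committee document for consistency.

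The cost is SAP wording, one derived variable and an extra table panel. No new data are needed.

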Immune complex-associated hypersensitivity reactions (e.g., serum sickness) may occur several days or weeks after the study treatment infusion and may be manifested as fever, arthritis, pruritus, and rash requiring no or limited treatment, or in some cases, requiring IV interventions.

Participants must be permanently discontinued from study treatment if anaphylaxis (based on criteria defined in [Sampson et al 2006](#) and summarized in [Appendix 2](#)) or other severe systemic

hypersensitivity reactions (e.g., those with symptoms of respiratory and/or cardiovascular systems requiring IV interventions) occur. The medical monitor should be contacted as soon as feasible if study treatment is permanently discontinued in any participant due to these reasons.

Participants who permanently discontinue treatment before the Week 4 visit should continue with all the remaining study visits.

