14.2 Appendix 2: Clinical Criteria for Diagnosing Anaphylaxis

Anaphylaxis is highly likely when any one of the following three criteria are fulfilled:

1. Acute onset of an illness (minutes to several hours) with involvement of the skin, mucosal tissue, or both (e.g., generalized hives, pruritus or flushing, swollen lips, tongue or uvula)
AND AT LEAST ONE OF THE FOLLOWING
 - a. Respiratory compromise (e.g., dyspnea, wheeze or bronchospasm, stridor, reduced peak expiratory flow, hypoxemia)
 - b. Reduced blood pressure or associated symptoms of end-organ dysfunction (e.g., hypotonia [collapse], syncope, incontinence)
2. Two or more of the following that occur rapidly after exposure to a likely allergen for that participant (minutes to several hours):
 - a. Involvement of the skin-mucosal tissue (e.g., generalized hives, itch or flush, swollen lips, tongue or uvula)
 - b. Respiratory compromise (e.g., dyspnea, wheeze or bronchospasm, stridor, reduced peak expiratory flow, hypoxemia)
 - c. Reduced blood pressure or associated symptoms (e.g., hypotonia [collapse], syncope, incontinence)
 - d. Persistent gastrointestinal symptoms (e.g., crampy abdominal pain, vomiting)
3. Reduced blood pressure after exposure to known allergen for that participant (minutes to several hours):
 - a. Infants and children: low systolic blood pressure (age specific) or greater than 30% decrease in systolic blood pressure*
 - b. Adults: systolic blood pressure of less than 90 mm Hg or greater than 30% decrease from that person's baseline

*Low systolic blood pressure for children is defined as less than 70 mm Hg from 1 month to 1 year, less than (70 mm Hg + [2× 3 age]) from 1 to 10 years, and less than 90 mm Hg from 11 to 17 years.

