### Vital signs

- Notable findings in vital signs

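### The SAP's low-systolic flag is narrower than the adult blood-pressure component in the protocol's anaphylaxis appendix, without explanation, so some infusion-day falls are left out of the notable-findings count

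*SAP*

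**What the plan says.** SAP 5.8.3 (Analysis of Vital Signs) defines a notable low systolic value by the rule "\leq 80$ mmHg and decrease by 20 mm Hg". A parallel diastolic rule needs 50 mmHg or less and a fall of 10 mmHg. The pulse rules use a percentage change; the blood-pressure rules do not. The section adds that "Notable findings in vital signs will be summarized by treatment and visit/timepoint".

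Protocol Appendix 2 (14.2), criterion 3b, reads "Adults: systolic blood pressure of less than 90 mm Hg or greater than 30% decrease from that person's baseline". Reduced blood pressure also appears in criteria 1 and 2 of that appendix, without an adult number. Protocol 6.6 gives the appendix a working role: "Participants must be permanently discontinued from study treatment if anaphylaxis" or another severe systemic hypersensitivity reaction occurs.

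On each of the three dosing days, SAP 4.6.3 says "vital signs should be assessed before initiation of infusion", then 15 minutes after the start, 15 minutes after the end of infusion and 1 hour after the end.

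The default baseline in SAP 6.1 is "the latest available valid measurement taken prior to the administration of study drug" at Week 0 (Day 1). Section 5.8.3 names no other.

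SAP 7.1.1 lists one vital-sign output for the interim analysis, the proportion of participants with notable findings. SAP 11.5 lists one for the SRC, "Notable findings in vital signs".

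**The concern.** Protocol 2.6 and 6.6 name systemic hypersensitivity to the infusion as a potential risk, and 6.6 lists hypotension among its signs. The trial takes three readings after the start of each infusion, or nine per participant over three infusions. Protocol 11.3.1 promises the number and proportion of participants with clinically important vital-sign values, and the notable-findings table is where the SAP delivers this.

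If the table's systolic cut-off lies well below the only adult figure in the protocol, it can show zero while some participants had falls that meet that figure. A reader of the interim or SRC outputs, who has no other listed vital-sign output, could take the zero to mean that no meaningful drop occurred.

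**Working it through.** **Inputs.** SAP rule: SAP 5.8.3. Protocol component: Appendix 2, criterion 3b. The documents give no baseline pressures, so those below are illustrative assumptions. Readings are whole mmHg, and the SAP's 20 mmHg fall is read as at least 20.

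**Rules**, with B the baseline and S the reading:
- SAP count: S ≤ 80 and B − S ≥ 20.
- Appendix 2 component: S < 90, or (B − S)/B > 0.30, which is S < 0.7 × B.

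**Direction of the gap.** Any reading the SAP counts has S ≤ 80, so S < 90, and it meets Appendix 2. The SAP rule is therefore wholly contained in the Appendix 2 component. The 30% limb reaches above 90 mmHg once B exceeds 90/0.7 = 128.6 mmHg.

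**Size of the gap:**

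| Baseline (mmHg) | SAP counts | Appendix 2 component met | Met but not counted |
|---|---|---|---|
| 95 | ≤ 75 | ≤ 89 | 76–89 |
| 100, 110 or 120 | ≤ 80 | ≤ 89 | 81–89 |
| 130 | ≤ 80 | ≤ 90 | 81–90 |
| 140 | ≤ 80 | ≤ 97 | 81–97 |
| 150 | ≤ 80 | ≤ 104 | 81–104 |
| 160 | ≤ 80 | ≤ 111 | 81–111 |

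**Examples.**
- 120 to 83: fall 37/120 = 30.8%. Both limbs are met; not counted.
- 140 to 95: fall 45/140 = 32.1%. The percentage limb is met; not counted.
- Fall needed to reach 80: from 120, 40/120 = 33.3%; from 140, 60/140 = 42.9%; from 160, 80/160 = 50.0%.

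**Baseline.** The choice matters on Days 15 and 29. Suppose the Day 1 value is 120, the Day 15 pre-infusion value is 140, and the pressure then falls to 95. Against Day 1 the fall is 25/120 = 20.8%; against the same-day value it is 32.1%. Only the second exceeds 30%.

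**Averaging.** SAP 6.3 averages vital signs taken on the same day, whereas 5.8.3 summarises by visit and timepoint. If 6.3 were applied across a dosing day, readings of 120, 78, 110 and 118 would average 426/4 = 106.5, and even the 78 would not be counted. Any added row should therefore say that it uses individual readings.

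**The case against.** The two passages serve different purposes. Appendix 2 is a diagnostic aid. Criterion 3b applies after exposure to an allergen already known for that participant, and in criteria 1 and 2 low pressure counts only alongside other organ involvement. SAP 5.8.3 is a general outlier table for all visits through Week 36, and nothing says it must mirror Appendix 2. This stands: the finding is an unexplained mismatch, not a contradiction.

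There are also other routes of capture. Protocol 8.2.3.1 requires a vital-sign value to be reported as an adverse event if it changes treatment, leads to intervention or is judged clinically significant. Infusion-related reactions are summarised and listed (SAP 5.8.1). Descriptive statistics by timepoint include the minimum, all vital signs are listed without a threshold, and the diastolic rule may catch some of the same episodes. This stands too and narrows the gap. What remains is a fall with no treatment change or intervention that the investigator does not judge clinically significant. The listing would show it and the minimum might, but no table would count it, and neither a listing nor descriptive statistics for vital signs is among the interim or SRC outputs.

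On the SRC, SAP 8 says its outputs follow a separate document dated 11 April 2024, which is not available here. SAP 2.1 has the SRC review all safety and laboratory data before escalation, and SAP 11.5 also gives it several adverse-event summaries. The escalation and stopping criteria are redacted, so nothing shows that this flag drives a decision.

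The Day 1 baseline in SAP 6.1 is an acceptable reading of the baseline in Appendix 2, which does not mention a same-day pre-infusion value. That choice needs stating; it is not an error.

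**Conclusion.** The point holds in a limited form. The SAP's systolic rule is strictly narrower than the adult blood-pressure component in protocol Appendix 2, and no reason is given. The uncounted band is 81–89 mmHg for baselines of 100 to 120 mmHg and widens to 81–97 at 140 and 81–104 at 150. How many participants would fall in it cannot be derived from the documents.

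The interim limb rests on the SAP's own list of outputs. By protocol 11.3.7 that analysis comes no earlier than Week 24, after dosing has ended, so there the effect is on reporting. The SRC limb further assumes that the separate document uses the 5.8.3 cut-offs, the only ones in the SAP.

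A reader might infer that the trial could miss anaphylaxis, or report no hypotension when its own definition says otherwise. The documents do not support either. The protocol has no definition of notable hypotension, a low reading alone is not anaphylaxis, and clinical recognition and adverse-event reporting do not depend on this table. The primary endpoint, incidence of TEAEs, is not derived from it. What is at stake is whether a zero in a descriptive table can be read as reassurance about a named infusion risk.

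**What to change.** Reconcile SAP 5.8.3 with protocol Appendix 2:

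- Keep the existing 80 mmHg row.
- Add one descriptive infusion-day row: participants with any individual, unaveraged reading after the start of infusion that meets the Appendix 2 adult blood-pressure component.
- State the baseline. Use the SAP 6.1 baseline, and show the same-day pre-infusion value as a second reference, labelled as an addition and not as Appendix 2 wording.
- Carry the row into the interim and SRC notable-findings outputs, and check that the separate SRC document agrees.
- List each counted reading beside the participant's adverse events on that day, with a footnote that a counted reading is not a diagnosis of anaphylaxis.

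This is a reporting change only and alters no treatment or discontinuation rule. It costs one row and a short listing from data already collected. The downside is that some isolated low readings without symptoms will be counted; the same-day listing lets a reader see which those are.
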